6.2. EMR data – Abstracted medical record data (per chart review)

Targeted chart reviews will be conducted at one point in time (towards the end of study follow-up period i.e.: Dec 2023) for all subjects enrolled in NET-PRO. Chart reviews will be undertaken to evaluate the following items:

- 1) Disease status (four-category variable defined below)
- 2) Clinical variables found to be insufficiently populated in the CDM
- 3) Other Clinical/pathological characteristics not recorded elsewhere (examples below)

The UICC has budgeted \$100 for chart abstraction for each case. In consultation with the clinician group, the consensus was that application of the RECIST criteria may be impracticable given current NET-PRO resources. Targeted chart abstraction will include a four-level categorization of disease status:

- 1) Disease control
- 2) Progression (no change in treatment)
- 3) Progression (with changes in treatment)
- 4) Indeterminate.

It was agreed that the clinical assessment and plan, would be the best source for identification of disease status for chart abstractors.

Other variables that may be selected for targeted chart review include clinical variables found to be insufficiently populated in the CDM. These may include interval lab values related to serum creatinine, BUN and eGFR (related to ascertainment of kidney toxicity for Aim 3) before and after PRRT cycles. It will also be important to collect tumor variables (i.e.: stage, grade, nodal status) for patients who were not identified from institutional tumor registries. An additional target for chart review may be other prognostic clinical/pathological characteristics not recorded elsewhere in the CDM or cancer registry data sources. For example information on mitotic count, chromogranin A (CgA) and Ki-67 proliferation index.

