3.2. Setting

We have identified 14 PCORnet partners (Table 1), chosen as subcontracted sites for the NET-PRO study based on their potential to prospectively recruit on average 215 patients over the 60 months study period. Importantly, all 4 partnering CRNs have previously collaborated in the PCORnet Cancer Collaborative Research Group, and 3 of the networks participated in a PCORnet Rapid Cycle Project of molecular targeted therapies to efficiently share individual-level data [44, 45]. All 4 CRN partners are able to link North American Association of Central Cancer Registries (NAACCR) required variables to their CDMs.

As shown in Table 1, 12 of our 14 PCORnet partners are affiliated with an NCI-designated Comprehensive Cancer Center. These are institutions dedicated to research in the development of more effective approaches to prevention, diagnosis and treatment of cancer involving a multidisciplinary team approach with skilled clinicians and specialized tumor boards. Importantly, these 14 partners also reflect the diverse clinical environments accessible to NET patients, including a mixture of high volume multidisciplinary specialist NET centers vs. some less specialized units, enabling the examination of the real-world experiences and outcomes of care across a variety of practice settings.

Table 1: List of 14 PCORnet partners

Clinical Site (Clinical Research Network (CRN))	NCI Cancer Center Designation
University of Iowa (GPC)*	Yes
Allina Health (GPC)	No
University of Kansas Medical Center (GPC)	Yes
Medical College of Wisconsin (GPC)	Yes
University of Texas Southwestern Medical Center (GPC)	Yes
University of Utah (GPC)	Yes
University of Florida (OneFlorida)	No
Mayo Clinic (STAR)	Yes
Medical University of South Carolina (STAR)	Yes
University of North Carolina at Chapel Hill (STAR)	Yes

Clinical Site (Clinical Research Network (CRN))	NCI Cancer Center Designation
Vanderbilt University Medical Center (STAR)	Yes
Ohio State University (PaTH)	Yes
University of Michigan (PaTH)	Yes
University of Pittsburgh Medical Center (PaTH)	Yes
*Includes the University of Iowa Coordinating Center (UICC)	

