- 3) **Progression-free survival (PFS).** Time to event data will be calculated from the index date (date of diagnosis) to the earliest of disease progression, death from any cause or end of study follow-up (12/31/2023). Acknowledging that patients may have more than one progression over the study period endpoints of median time to first progression (time from initiation of first-line therapy to progression) and time to second progression (time from second-line therapy initiation to progression) will be observed from targeted chart reviews at annual intervals. In collaboration with our clinician group we have discussed the various limitations of the application of the RECIST 1.1 criteria in NETs. These limitations include an overemphasis on tumor progression (given the low proliferation rate of GEP-NETs, monitoring changes in tumor size is suboptimal), and RECIST 1.1 criteria do not reflect overall tumor load or response to therapy in metastatic patients (i.e.: issues with clinical significance of radiologic progressions). Optimizing the management of NET patients therefore requires considering clinical, biological, and pathological aspects of the tumor. We have therefore chosen to categorize disease progression as DISEASE CONTROL (complete or partial response & stable disease), PROGRESSION (with no treatment change), PROGRESSION (with treatment change), and INDETERMINATE. This clinician-anchored approach has been found to be an optimal and valid method (versus RECIST1.1) for evaluating real-world tumor burden endpoints from EMR data [55].
[Time Frame: median time to progression, assessed annually via chart review]
- 4) **Overall Survival (OS).** Time to event data will be calculated from the date of diagnosis (index date) to the date of death from any cause, or end of study follow-up (12/31/2023). Death and vital status (death date, cause of death) will be pulled from the death table, and death cause table in the CDM. This data may be supplemented from site linkage to the social security death index or cancer registry sources (where possible). Given the prospective nature of the study we also have potential for passive surveillance/follow-up with participant/next of kin with information collected on our follow-up questionnaires.
[Time Frame: Up to 5 years]

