9. STATISTICAL ANALYSIS PLAN

9.1. General Statistical Approach

Continuous variables will be summarized using descriptive statistics such as mean, standard deviation, median, minimum and maximum. Categorical variables will be summarized by count and percentage. Group comparisons will be assessed using chi-squared or Fisher's exact tests for categorical variables, and an analysis of variance or Kruskal-Wallis tests for continuous variables where appropriate. Adjustment for covariates listed in Tables 2 and 3 will be explored for each analysis as needed to account for potential confounding effects. Time-dependent covariates will be incorporated to capture changes in covariates across time, as necessary. Inclusion of random effects to account for potential clustering of patients treated at the same study site will be explored. Depending on the rate and pattern of missing data, multiple imputation methods may be considered to account for data missing at random or attributable to non-ignorable drop-out [56]. Planned study outcomes are summarized in Table 4.

9.1.1. Aim 1

Mixed effects regression models will be utilized to assess changes in HRQoL and symptoms within and between groups (i.e.: different treatment regimens) over time. Random effects will be employed to account for the longitudinally correlated nature of repeated questionnaire measurements. Should completion of questionnaires deviate from the planned assessment time points, a spatial power covariance structure will be included to account for the unequal time spacing between assessments within a patient.

9.1.2. Aim 2

Multinomial logistic regression models will be used to identify which patient, clinical, and tumor characteristics (Table 2), and patient attitudes and beliefs (Table 3) influence selection of treatment regimens for each line of treatment. The conditional Cox regression model proposed by Prentice, Williams, and Peterson (PWP) will be used to simultaneously model the gap times between initial diagnosis and first progression and between subsequent progressions as a function of the prognostic factors of interest for progression-free survival. The baseline hazard is expected to differ for first-line therapy and for subsequent lines of therapy, thus event-specific estimates will be obtained. A robust sandwich estimator will be used to account for potential dependencies within patients. Overall survival will be evaluated using a Cox regression model.

9.1.3. Aim 3

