15.1. Risk to Human Subjects

15.1.1. Study Procedures, Materials and Potential Risks

A potential risk to subjects is to their privacy and confidentiality should our efforts to protect this be inadvertently breached. There is the potential that participants will experience some discomfort from responding to questions about their health and health care. Any unauthorized disclosure of identifiable data may also induce the feeling of distress. However, this is not an intervention study, and study subjects may choose to not answer any questions or withdraw from the study at any time.

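### Progression is read from routine notes with no common assessment schedule and event-free time runs to 12/31/2023, so a regimen that is monitored more closely can look worse on PFS when true control is equal

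*Protocol*

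**What the plan says.** Protocol 6.2 sets RECIST aside, since "the consensus was that application of the RECIST criteria may be impracticable given current NET-PRO resources", and uses a four-level disease status instead. On where abstractors should find that status, it says "the clinical assessment and plan, would be the best source for identification of disease status for chart abstractors".

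Protocol 7.2 (item 3) defines PFS from diagnosis "to the earliest of disease progression, death from any cause or end of study follow-up (12/31/2023"). Under 9.1.2, a Prentice-Williams-Peterson (PWP) conditional Cox model will "simultaneously model the gap times between initial diagnosis and first progression and between subsequent progressions". Section 8.3 compares PRRT regimens on disease progression, and 9.1.3 carries the Aim 1 and 2 methods over to Aim 3.

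No section sets a visit or imaging interval for disease assessment. That fits the design: 15.1.1 notes that "this is not an intervention study". The sites are described in 3.2 as "a mixture of high volume multidisciplinary specialist NET centers vs. some less specialized units".

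The only timing statements concern the chart review, and they conflict. Section 6.2 says "Targeted chart reviews will be conducted at one point in time", while 7.2 says that progression times "will be observed from targeted chart reviews at annual intervals".

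**The concern.** A progression found in routine care is known only to have occurred between the last assessment that showed control and the first that showed progression. If the detection date is used as the event time, the delay counts as progression-free time. With regular assessments the delay averages half the interval.

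End-date censoring adds to this. A patient who progresses after the last assessment is counted as progression-free up to 12/31/2023, and the longer the gap between assessments, the more such time accrues.

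If both effects are equal across regimens, they largely cancel in a comparison. If one regimen brings closer follow-up than another, they do not cancel, and the hazard ratio moves against the closely watched regimen.

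The planned safeguards do not reach this. Covariate adjustment (9.3) targets factors linked to treatment selection. Random effects for site and provider (9.4) may absorb part of a between-site difference, but not a difference between regimens within a site. Abstractor training (6.2.2) standardises how notes are read, not when patients are assessed.

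**Working it through.** **Inputs from the Protocol (9.2.2, Table 6):** 1:1 allocation, 48 months of uniform accrual (A), 12 months of further follow-up (F), no loss to follow-up, two-sided 5% log-rank test. Medians of 12 v 24 months with 45 or 50 per arm, and 24 v 36 months with 175 or 190 per arm.

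**Step 1: reproduce Table 6.** With exponential PFS and λ = ln 2 / median, the probability of an observed event is

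P = 1 − [exp(−λF) − exp(−λ(A+F))] / (λA).

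This gives P = 0.831, 0.617 and 0.482 for medians of 12, 24 and 36 months. Expected events are 50 × (0.831 + 0.617) = 72.4 and 175 × (0.617 + 0.482) = 192.4 (the latter from unrounded P). A Lakatos-type stepwise calculation gives power of 0.795, 0.835, 0.801 and 0.832, against the stated 0.79, 0.83, 0.80 and 0.83. The power table is sound.

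**Step 2: detection lag.** The assessment intervals of 3, 6 and 12 months are assumptions. The mean lag is interval / 2, that is 1.5, 3 and 6 months. Simulated observed medians are:

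| True median | every 3 months | every 6 months | every 12 months |
|---|---|---|---|
| 12 months | 13.5 | 15.1 | 18.4 |
| 24 months | 25.6 | 27.1 | 30.2 |

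**Step 3: two regimens with identical true progression.** Exponential event times, follow-up uniform over 12–60 months, assessments at a random offset and then at a fixed interval, progression dated at the next assessment. The test is a two-sided 5% log-rank test, used because it is the score test of an unadjusted two-group Cox model for first progression. HR is less often over more often assessed.

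| Intervals and method | Median 24, 175/arm | Median 12, 50/arm |
|---|---|---|
| Equal intervals, end-date censoring | about 5%, HR 1.00 (190/arm) | 5–6%, HR 1.00 |
| 3 v 6, end-date | 7–8% | 7–8% |
| 6 v 12, end-date | 15–19% | 15–19% |
| 3 v 12, end-date | 36%, HR 0.80 | 30%, HR 0.72 |
| 3 v 12, end-date, 30% of events exactly dated deaths | about 19% | about 15% |
| 3 v 12, censored at last assessment | about 11%, HR 0.90 | about 15–20%, HR 0.79 |
| 3 v 12, midpoint dating, end-date kept | 12%, HR 0.89 | – |
| 3 v 12, midpoint dating, censored at last assessment | 5–6%, HR 0.97–1.00 | 5–6%, HR 0.97–1.00 |

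For the 3 v 6 and 6 v 12 rows, the percentages are ranges over both settings.

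**Step 4: would annual abstraction help?** With detection dates rounded up to a yearly grid, 3 v 12 months still gives an HR for the more often assessed arm of 1.24 (median 24, 190 per arm) and 1.29 (median 12, 50 per arm). It is declared significantly worse in 40% and 30% of replicates, against a nominal 2.5%. Reading charts annually does not give patients common assessment times.

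**Reading the table.** At median 24 months, changing the censoring alone takes 36% to 11%, and changing the dating alone takes it to 12%. Only the two together bring the error back near 5%. Second and later PWP gaps were not simulated. Their starting points are themselves detection dates, so uncertainty enters at both ends.

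**The case against.** The case against is substantial, and several parts of it stand.

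- **No dating rule is written.** Section 6.2 names the source of disease status, not of its date. A reader might infer that the Protocol orders progression to be dated by the clinician's note. It does not; that is only the natural reading of 6.2 with 7.2.
- **The intervals are assumed.** A reader might infer that regimens are known to be monitored differently. The documents describe variety between sites, not between regimens, and 9.4 plans site and provider random effects. At 3 v 6 months the inflation is slight.
- **No confirmatory test is at risk.** A reader might infer that a planned 5% log-rank test fails. Log-rank appears only in the power illustration of 9.2.2, which calls its scenarios hypothetical and the Aim 2 analyses exploratory. PFS is a secondary outcome in 7.2 and Table 4.
- **Deaths dilute the effect.** PFS includes deaths dated from death tables. If these are 30% of events, the excess is roughly halved.
- **Later documents may deal with it.** The chart form and abstraction manual are still to be developed (6.2.1, 6.2.2), and 9.3 says the analysis plan will be refined. This does not fully answer the point. End-date censoring is already written into 7.2 and accounts for much of the bias. If the date of the last assessment showing control is not abstracted, no analysis plan can recover it without reopening the charts.

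The source cited in 7.2 for the clinician-anchored approach is offered in support of the progression criterion against RECIST. It is not offered as an answer to unequal timing of assessments.

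**Conclusion.** The concern holds in a conditional form. Status from routine notes, no common assessment schedule and end-date censoring together leave the regimen and sequence comparisons of progression open to bias against the more closely monitored regimen. With equal true control, the false-positive rate is about 30–36% (HR 0.72–0.80) at 3 v 12 months, 15–19% at 6 v 12 and 7–8% at 3 v 6. It is about 15–19% at 3 v 12 if 30% of events are exactly dated deaths.

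These figures rest on assumed intervals that differ wholly by regimen, exponential times, dating at detection, and no adjustment. With equal assessment frequency there is no bias between regimens. The consequence is distorted hazard ratios in secondary and exploratory comparisons. Those still matter, because 15.1.3 expects the results to guide which treatments are used first. The change should be made before the chart form is fixed, but the study does not fail without it.

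**What to change.** 1. **Chart form (6.2.1).** For every patient, record the date of the last assessment showing disease control. For each progression, also record the date of the first assessment showing it.
2. **PFS definition (7.2).** Censor patients without progression or death at their last disease assessment instead of at 12/31/2023, and keep deaths at their exact date. State how a progression is dated.
3. **Analysis (9.1.2, and 9.1.3 by extension).** Add a prespecified sensitivity analysis of first progression, either interval-censored between the two dates or with midpoint dating in the Cox/PWP model. Item 2 alone leaves part of the bias, and so does midpoint dating with the fixed end date kept.
4. **Chart review timing.** Reconcile the single review in 6.2 with the annual reviews in 7.2.

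None of this asks for visits to be scheduled.

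The cost is one or two extra dates per chart, one extra model and slightly wider intervals. Counting every assessment per patient-year by regimen would show directly whether monitoring differs, but is optional given the budget of $100 per case. Reopening all charts later at that rate would cost about 3,010 × $100 = $301,000.

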6.2.1. Chart review form

The UICC will develop, test and distribute to sites an agreed REDCap form, which will include the minimum data elements required for chart abstraction. This form will be designed with input from all NET-PRO stakeholder groups (i.e.: clinician, informatics and patient advocacy committees).

6.2.2. Chart review training

All research team members engaged in chart review and abstraction will receive training from the UICC in an effort to standardize the process. The UICC will develop a manual that will provide detailed instruction on the information and variables to be collected.

6.3. Patient surveys

Table 3 outlines the measures that will be collected from the baseline and follow-up surveys which will be administered through the PHR. The UICC has prepared a data dictionary for the baseline survey. Data dictionaries will also be made available for the follow-up surveys.

Whilst many of the current survey items are derived from validated instruments, or have been used in empirical research studies, we are receiving input from the clinician group and patient advocacy organization committees to adapt and tailor many of these items to a NET population. We anticipate that several physical and psychosocial themes may be missing from the HRQoL questionnaires that we are using which may be important to patients and/or help clinicians in their patient interactions. Therefore, in working with our patient partners and clinician groups we may identify further themes, concepts and items impacting on HRQoL and incorporate these additional measures into the baseline and study follow-up questionnaires.

Table 3: Overview of concepts and measures examined on the baseline and follow-up surveys

Concept/measure	Baseline Survey	Follow-up Surveys
Sociodemographic data (date of birth, sex and gender orientation, race, marital status, ethnicity, state of residence, household income, highest level of educational attainment, health literacy)	X	
Height and weight	X	X
Health Related Quality of Life, QLQ-C30, QLQ-GINET21, Other impacts of cancer (worry, other life events)	X	X
Norfolk Carcinoid Symptom Score [47]	X	X
History of chronic conditions (20-item checklist)[48]	X	
Preferences and attitudes (quality vs quantity of life [49], preferred decision-making role [50, 51], family's role in decision-making)	X	
Attitudes (fatalistic thinking, spirituality) [52], Experiences of care (physician communication, coordination and responsiveness of care [53], actual decision-making role [50]	X	X
Self-reported treatments, including over-the-counter medications and supplements	X	X

6.4. Patient study website navigation

Logins and website navigation data (dates and times that features were accessed) from subject use of the study website will be collected; website data collected prior to consent will also be linked to other subject data. This information will be useful in exploring uptake of developed features (see 9.3) and in identifying any problems with use of the website.

7. STUDY OUTCOMES

Table 4 summarizes the primary and secondary outcomes of the NET-PRO study by project aims.

7.1. Primary Outcomes

- 1) **European Organization for Research and Treatment of Cancer - Quality of Life Questionnaire (EORTC QLQ-C30).** The EORTC QLQ-C30 is one of the most widely used HRQoL questionnaires in cancer research. A validated tool, it consists of 30 questions with a 4-point Likert scale (from “not at all” to “very much”) incorporating five functional scales (physical, role, cognitive, emotional, and social), three symptom scales (fatigue, pain, and nausea and vomiting), a global health status / QoL scale, and a number of single items assessing additional symptoms commonly reported by cancer patients (dyspnea, loss of appetite, insomnia, constipation and diarrhea) and perceived financial impact of the disease. Responses to the QLQ-C30 will be linearly transformed to a 0-100 scale using EORTC guidelines, a higher score represents a higher (“better”) level of functioning, or a higher (“worse”) level of symptoms. A mean difference of 10 points (positive or negative) has been widely accepted as the minimal clinically important difference (MCID) for the EORTC QLQ-C30 [58]. A specific MCID for carcinoid syndrome and NET has not been identified. However a recent study in advanced colorectal cancer has indicated MCIDs for improvement (deterioration) ranged from 6 to 18 (-11 to -5) points for within-group change and 5 to 15 (-10 to -4) for between-group change for the EORTC QLQ-C30, with summarized MICDs (in absolute values) per scale mostly ranging from 5 to 10 points [59]. An MCID was not identified in the literature for the QLQ-GI.NET21 module.

[Time Frame: Change in mean score across baseline, 6, 12, and 18 month time points.]

- 2) **European Organization for Research and Treatment of Cancer - Quality of Life Questionnaire - Neuroendocrine Carcinoid Module (EORTC QLQ-GI.NET21)** The EORTC QLQ-C30 can be used in conjunction with the EORTC QLQ-GI.NET21 specific questionnaire, which comprises a total of 21 items: four single-item assessments relating to muscle and/or bone pain (MBP), body image (BI), information (INF) and sexual functioning (SX), together with 17 items organized into five proposed scales: endocrine symptoms (ED; three items), GI symptoms (GI; five items), treatment-related symptoms (TR; three items), social functioning (SF21; three items) and disease-related worries (DRW; three items). Responses to the QLQ-GINET21 will be linearly transformed to a 0-100 scale using EORTC guidelines, with higher scores reflecting more severe symptoms.

[Time Frame: Change in mean score across baseline, 6, 12, and 18 month time points.]

- 3) **Sequencing of treatment regimens from electronic medical records.** This will involve identifying which treatments a patient used during their follow-up, and also in what order they received treatment. Dates and types of therapy initiated will be pulled from each patients EMR in reference to the patient’s index date (date of diagnosis). We will also be asking patients about their treatments (self-reported) in the baseline survey to ascertain potential missed therapies in the EMR. We will be comparing the frequency (N) and proportion (%) of use of a variety of therapies (i.e.: SSAs, bevacizumab, cytotoxic chemotherapy, everolimus, Interferon alpha, embolization, PRRT, small molecule TKIs) and the effects of their ordering/sequencing on outcomes of symptom burden and HRQoL.

[Time Frame: Up to 5 years, baseline to end of follow-up]

- 4) **Renal function.** Glomerular filtration rate (GFR) is the best overall index of kidney function. Normal GFR declines with age, and varies according to sex, race and body size. We will calculate creatinine clearance loss [54] by combining individual level CDM and enrollment questionnaire data on sex, race, height, weight and serum creatinine mg/dl laboratory values at regular intervals before and after PRRT cycles until the end of follow-up.

[Time Frame: Change in eGFR from baseline to end of follow-up.]

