4. STUDY DESIGN

4.1. Time anchors for study cohort

Study Period: 01/01/2019 to 12/31/2023 (5 years, max 60 months follow-up)

Index Date: Date of diagnosis of eligible NET tumor in the study period

Source Data Range: 01/01/2017-12/31/2023 (7 years, includes 2-year look-back period)

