4.2. Inclusion/Exclusion Criteria

To be eligible for this prospective cohort study subjects must meet **all** of the following criteria:

- i. Incident GEP-NET/Lung NET diagnosis*(see [Appendix A](#))
- ii. Diagnosed 01/01/2019-12/31/2023
- iii. No known prior GEP-NET/Lung NET diagnosis
- iv. Aged ≥ 18 years at diagnosis
- v. At least one site encounter within the study period of January 1, 2019 to December 31, 2023

* See [Appendix A](#) for a full list of International Classification of Diseases, Ninth Revision, Clinical Modification (ICD-9-CM), The International Classification of Diseases, Tenth Revision, Clinical Modification (ICD-10-CM) codes used to define a NET diagnosis. This appendix also lists the ICD-O-3 site codes and eligible histology codes for implementation in tumor registry data sources.

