8.1. Aim 1 (Frequency of treatment regimens)

In this aim we will describe the frequencies of treatment regimens by line of therapy and multi-line sequences. Information from Aim 1 will also be used – with input from the Patient Advocacy Committee (PAC) and Clinician Group – to finalize the comparators for Aims 2 and 3.

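### Primary outcome 3 counts therapies as a crude N and % over follow-up of about 0 to 60 months, so later-line use is under-counted relative to early use by an amount the protocol cannot fix

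*Protocol*

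**What the plan says.** Section 7.1, item 3 (sequencing of treatment regimens) is a primary outcome. It sets out what is counted: "This will involve identifying which treatments a patient used during their follow-up". It also sets out the measure: "We will be comparing the frequency (N) and proportion (%) of use of a variety of therapies", together with the effects of ordering on symptoms and HRQoL. The horizon is "Time Frame: Up to 5 years, baseline to end of follow-up". The same item says that "Dates and types of therapy initiated will be pulled from each patients EMR", referenced to the date of diagnosis.

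Section 9.1 adds the general rule that "Categorical variables will be summarized by count and percentage". Section 8.1 says that Aim 1 will "describe the frequencies of treatment regimens by line of therapy and multi-line sequences", without naming a denominator.

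On dates, Section 4.2 requires "Diagnosed 01/01/2019-12/31/2023". Section 4.1 ends both the study period and the source data on 12/31/2023, with at most 60 months of follow-up. Section 7.2, items 3 and 4, end PFS and OS follow-up on that same day. Section 6.1 gives a different window: CDM data to roughly 36 months after the patient joined.

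**The concern.** A patient diagnosed in January 2019 has up to 60 months in which a second- or third-line therapy can be recorded. A patient diagnosed late in 2023 has almost none, yet counts equally in the denominator. The resulting percentage is neither a one-year nor a five-year figure. The shortfall also differs by therapy: slight for treatment given at diagnosis, larger for treatment that usually comes after progression.

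This matters because later-line sequencing is the question the study was set up to answer. Table 4 lists sequencing as the Aim 2 primary outcome, and Section 2.1 has Aim 2 compare how often subsequent treatments are received. The protocol already treats PFS and OS, which share the index date and cut-off, as time-to-event outcomes. Treatment use has the same structure but is not treated that way.

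**Working it through.** **The plan's own figures.** 14 sites × 215 = 3,010 patients. 10% PRRT use gives 301, stated as about 300. 60% of 300 = 180, as stated. These reproduce. The 10% carries no time horizon, and the protocol states no figure for under-counting.

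**Inputs from the protocol.** Diagnosis window 01/01/2019 to 12/31/2023 (Section 4.2). Data and follow-up end 12/31/2023 (Sections 4.1 and 7.2). Hypothetical median PFS of 12, 24 and 36 months (Section 9.2.2, Table 6).

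**Assumptions.** Diagnoses are spread evenly over the 60 months, so follow-up F is uniform on 0-60 (mean 30 months, 20% of patients under 12 months). Deaths are ignored. The time T from diagnosis to a therapy is not given in the protocol, so it is varied.

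**Formula.** Of patients who would start a therapy within 60 months, the share that a crude count captures is P(T ≤ F | T ≤ 60). For a fixed delay t this is 1 − t/60.

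| Delay t (months) | 1 | 2 | 3 | 12 | 18 | 24 | 30 | 36 |
|---|---|---|---|---|---|---|---|---|
| Captured | 98% | 97% | 95% | 80% | 70% | 60% | 50% | 40% |
| Lost | 2% | 3% | 5% | 20% | 30% | 40% | 50% | 60% |

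For an exponential T with rate L, captured = [1 − (1 − e^(−60L))/(60L)] / (1 − e^(−60L)). With a median of 12 months, 60L = 3.466 and e^(−3.466) = 0.031, so captured = (1 − 0.969/3.466)/0.969 = 0.74. Medians of 24 and 36 months give 0.64 and 0.59. Starts spread evenly over 60 months give 0.50.

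**Later lines triggered by progression.** Assume first-line therapy at 2 months, exponential PFS with the protocol's hypothetical medians, and the next line at progression (simulation, 2,000,000 patients per scenario). Cells show the share captured for medians of 12 / 24 / 36 months.

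| Follow-up scenario | Second line | Third line |
|---|---|---|
| Uniform diagnosis, cut at 12/31/2023 | 71 / 61 / 57% | 52 / 42 / 39% |
| Enrolment about 4/2022 to 12/2023, diagnosis evenly spread before it, same cut-off | 82 / 71 / 67% | 62 / 51 / 46% |
| Same enrolment, data to 36 months after joining, capped at 60 from diagnosis | 98 / 95 / 94% | 94 / 89 / 87% |

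The losses are therefore 29-43% and 48-61% in the first row, 18-33% and 38-54% in the second, and about 2-13% overall in the third.

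**Illustration.** If 10% (301 patients) were the true 60-month PRRT use, the crude figure would be 301 × 0.744 = 224 (7.4%) with an exponential median of 12 months, 301 × 0.638 = 192 (6.4%) with a median of 24, and about 150 (5%) with evenly spread starts.

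**Can the third row happen?** Section 11, Table 8 projects the first enrolment for 4/29/2022, so 36 months after joining is about April 2025 at the earliest. Section 6.1 requests the data in late 2023, Section 6.2 does chart review once, around December 2023, and Table 8 closes data collection on 6/30/2024. Even the first participant would have only about 20 months from joining to 12/31/2023, or about 26 months to 6/30/2024.

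**The case against.** The strongest reply is that the protocol never claims to estimate five-year use. The outcome concerns which treatments are given and in what order, described by line. If the percentages are taken among patients who start a given line, N and % are sound. Section 9.1 models selection for each line by multinomial regression and progression by the PWP model, and Section 9.2.2 calls the Aim 2 analyses exploratory. The count-and-percentage sentence in Section 9.1 is generic, and a separate analysis plan may refine it. Self-reported treatments are also collected on the follow-up surveys (Table 3), which can add some information after 12/31/2023.

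Much of this stands and limits how serious the point is. It does not remove it. The crude N and % is written into the definition of a primary outcome, with follow-up of up to 5 years and no denominator by line.

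A reader might infer more than the documents support:

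- **That later-line use is under-reported by about half.** This needs a delay near 30 months, evenly spread starts, or third-line use. The protocol gives no time from diagnosis to PRRT or any later line.
- **That therapies are put in the wrong order.** No reversal is shown. With a constant start rate, true five-year use of 10, 20, 30 and 50% appears as 5.1, 10.4, 15.9 and 27.9%, in the same order.
- **That contrasts by site, grade or tumor type are distorted.** This requires follow-up to differ between those groups, and nothing in the protocol shows that it does.
- **That comparators for Aims 2 and 3 will be chosen on distorted percentages.** Table 8 projects that decision for 5/31/2022, about a month after the projected first enrolment, so end-of-study percentages cannot drive it.

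**Conclusion.** The point holds in direction. On the protocol's own dates, the stated measure mixes use with length of observation and under-counts later-line therapy relative to therapy begun soon after diagnosis. Its size is not fixed by the documents. Under uniform diagnosis, a 12/31/2023 cut-off and no deaths, the loss is about 2-5% for starts at 1-3 months and about 20-60% for delays of 12-36 months. It would be about 2-13% for second and third line under the Section 6.1 window, which the stated schedule does not reach and which conflicts with Sections 4.1 and 7.2. This is a cheap improvement to a descriptive primary outcome. It does not invalidate the Aim 2 or Aim 3 models.

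**What to change.** In Section 7.1, item 3, report use of each therapy and each line as cumulative incidence at fixed times from diagnosis, for example 1, 2 and 3 years, with death as a competing event and censoring at the end of observed follow-up.

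Take delayed entry at enrolment into account. Patients may join well after diagnosis and must be alive to consent, so an estimate that places everyone at risk from diagnosis understates early death. The text should also say how treatment starts between diagnosis and enrolment are used, since they are seen only in patients who survived to join.

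Keep N and % for the mix of regimens among patients who start a given line, and state that denominator in Sections 7.1 and 8.1. Reconcile the data window in Section 6.1 with the end dates in Sections 4.1 and 7.2.

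The cost is a few sentences of text and standard software, using start dates already collected. The downside is that estimates at longer horizons rest on the earlier-diagnosed patients and have wider intervals.
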